8.1.3. Follow Up Period

For follow-up procedures see the Schedule of Activities in **Section 1.3 Assessments** in **Section 8.2.**

8.1.4. Unscheduled Visits

In the event that the subject will return to clinic at a time other than a regularly scheduled study visit, the visit will be regarded as an unscheduled visit. Assessments at unscheduled visits are at the discretion of the Investigator. All pertinent findings, including adverse events or changes in medications, will be noted in the subject medical records.

8.2. ASSESSMENTS

Every effort should be made to ensure that the protocol-required tests and procedures are completed as described. However, it is anticipated that from time to time there may be circumstances outside of the control of the investigator that may make it unfeasible to perform the test. In these cases, the investigator will take all steps necessary to ensure the safety and well-being of the subject. When a protocol-required test cannot be performed, the investigator will document the reason for this and any corrective and preventive actions that he or she has taken to ensure that normal processes are adhered to as soon as possible. The study team will be informed of these incidents in a timely manner.

8.2.1. Safety Assessment

Safety assessments will include collection of adverse events (AEs), serious adverse events (SAEs), vital signs and physical examination, electrocardiogram (ECG [12-lead]), laboratory assessments, including pregnancy tests and verification of concomitant treatments.

8.2.1.1. Pregnancy Testing

All pregnancy tests used in this study, either urine or serum, must have a sensitivity of at least 25 mIU/mL. For female subjects of childbearing potential, a negative pregnancy test is required before receiving CX-4945 (1 negative pregnancy test at screening and 1 negative pregnancy test at day 1 prior CX-4945 dosing). Following a negative pregnancy test result at screening, appropriate contraception must be commenced. For women of childbearing potential subject should have used hormonal or barrier method of birth control; or abstinence as highly effective contraception from screening until at least 2 weeks after the last study drug administration.

Subjects who are found to be pregnant during the screening period will be a screen failure. Subjects who are found to be pregnant during the treatment period will be asked to discontinue study treatment.

8.2.1.2. Adverse Events (AEs)

Assessment of AEs will include the type, incidence, severity (graded by the CTCAE version 5.0) timing, seriousness, and relatedness. For AE assessment details, see **Section 8.3.3**. Investigator will follow-up for any AEs/SAEs at Day 14.

8.2.1.3. Vital Signs and Physical Examination

Subjects will have a full physical examination to include an examination of all major body systems, height (at screening only), weight (at screening only), blood pressure, respiration rate, SpO₂, temperature and heart rate, which may be performed by a physician, registered nurse or other qualified health care provider, as acceptable according to local regulation. The physical examination, assessing the subject's overall health and physical condition, will be performed according to the site's SOPs. Changes from baseline abnormalities should be recorded at each subsequent physical examination. New or worsened abnormalities should be recorded but only clinically significant abnormalities will be recorded as an AE.

Pulse oximetry should be collected prior to collection of the blood pressure, pulse rate, and temperature. Oxygen levels should be evaluated on the finger in accordance with the site's standard procedures. All abnormalities will be evaluated by the study physician.

Blood pressure, heart rate, respiration rate, and temperature should be recorded after approximately 5 minutes rest.

8.2.1.4. Laboratory Safety Assessment

Hematology and blood chemistry will be drawn at the time points described in the Schedule of Activities (see **Section 1.3**) and analyzed at local laboratories. Unscheduled clinical labs may be obtained at any time during the study to assess any perceived safety concerns. Samples for hematology, blood chemistry, coagulation, pregnancy and urinalysis will be analyzed by the site's local laboratory.

Table 2. Safety Laboratory Tests

Hematology	Biochemistry	Coagulation	Urinalysis	Pregnancy Test
Hemoglobin	ALT	PT	color, appearance, specific gravity, pH, protein, glucose, occult blood, ketones, leukocyte esterase, nitrite, bilirubin, urobilinogen	For female subjects of childbearing potential, serum or urine
Hematocrit	AST	INR		
RBC	ALP			
Platelets	LDH			
WBC	Total Protein			
Absolute Neutrophils	Sodium			

Hematology	Biochemistry	Coagulation	Urinalysis	Pregnancy Test
Absolute Lymphocytes	Potassium		microscopic examination of urine sediment	
Absolute Monocytes	BUN			
Absolute Eosinophils	Chloride			
Absolute Basophils	Total Calcium			
	Magnesium		Serology	
	Phosphorus		Anti-HIV	
	Bicarbonate		Anti-HCV	
	Total bilirubin		Anti-HBV	
	Creatinine (serum)			
	Albumin		Others	
	C-reactive protein (CRP)		Anti-SARS-CoV2	
	Creatine Phosphokinase (CPK)			
	Creatine kinase-MB(CK-MB mass)			
	Triglyceride			
	Total Cholesterol			
	Glucose AC			
	Uric Acid			
	γ-GT			

8.2.1.5. **Electrocardiogram (ECG)**

An ECG will be done at Screening, Day 1, Day 3, Day 5, and at Day 6. It is preferable that the machine used has a capacity to calculate the standard intervals automatically, including QT and QTc interval. At each time point (see the Schedule of Activities), if the significant abnormalities (>Grade 2) in ECG intervals are revealed, then the ECGs should be re-evaluated by a qualified person at the site for confirmation as soon as the finding is made, including verification that the machine reading is accurate.

8.3. **ADVERSE EVENTS (AES) AND SERIOUS ADVERSE EVENTS (SAEs)**

The Investigator is responsible for the detection and documentation of events meeting the criteria and definition of an AE or SAE, as provided in this protocol. During the study when there is a safety

evaluation, the Investigator or site staff will be responsible for detecting, documenting and reporting AEs and SAEs as detailed in this Section of the protocol.

8.3.1. Definitions of AE

An AE is defined as any unfavorable or unintended sign, symptom, or disease that occurs or is reported by the subject to have occurred, or a worsening of a pre-existing condition. An AE may or may not be related to the study treatment.

AEs will be elicited through direct questioning and subject reports. Any abnormality in physical examination findings or laboratory results that the investigator believes is clinically significant (CS) to the research subject and that occurred after initiation of the first study treatment will be reported as AEs. Abnormal findings that are NOT clinically significant should not be recorded as an AE.

8.3.2. Definition of SAEs

A SAE is defined as any AE that:

- Results in death
- Is life threatening (the subject is at immediate risk of dying from the AE)
- Requires subject hospitalization or prolongs existing hospitalization
- Results in persistent or significant disability/incapacity
- Is a congenital anomaly/birth defect

Important medical events that may not result in death, be life-threatening, or require hospitalization may be considered a SAE when, based upon appropriate medical judgment, they may jeopardize the subject or subject and may require medical or surgical intervention to prevent one of the outcomes listed in this definition.

8.3.3. Classification of AEs

8.3.3.1. Severity of AE

The guidelines outlined in CTCAE v5.0 will be used for assessing the intensity of the event. The general guidelines for assessing the AE grade appear below. Full guidelines may be obtained at <http://evs.nci.nih.gov/ftp1/CTCAE>.

Table 3. CTCAE v5.0 General Guidelines

Grade	Description
Grade 1	Mild; asymptomatic or mild symptoms; clinical or diagnostic observations only; intervention not indicated.

Grade 2	Moderate; minimal, local or noninvasive intervention indicated; limiting age- appropriate instrumental activities of daily living (ADL)*.
Grade 3	Severe or medically significant but not immediately life-threatening; hospitalization or prolongation of hospitalization indicated; disabling; limiting self care ADL†.
Grade 4	Life-threatening consequences; urgent intervention indicated.
Grade 5	Death related to AE.

*Instrumental ADL refer to preparing meals, shopping for groceries or clothes, using the telephone, managing money, etc.

†Self care ADL refer to bathing, dressing and undressing, feeding self, using the toilet, taking medications, and not bedridden.

-Common Terminology Criteria for Adverse Events (CTCAE), v5.0: November 27, 2017

8.3.3.2. Causality Assessment

AEs will be assigned a relationship (causality) to the study treatment. The Investigator will be responsible for determining the relationship between an AE and the study treatment. The type of event, organ system affected, and timing of onset of the event will be factors in assessing the likelihood that an AE is related to the study treatment. Relationship of AEs to study treatment will be classified as follows:

- Definitely related:** This category applies to those AEs that the Investigator feels are incontrovertibly related to the study treatment. An AE may be assigned an attribution of definitely related if or when it meets all of the following criteria: (1) it follows a reasonable temporal sequence from administration of the study treatment; (2) it could not be reasonably explained by the known characteristics of the subject's clinical state, environmental or toxic factors, or other modes of therapy administered to the subject; (3) it follows a known response pattern to treatment with the study treatment.
- Probably related:** This category applies to those AEs which, after careful medical consideration at the time they are evaluated, are felt with a high degree of certainty to be related to the study treatment. An AE may be considered probable if or when (must have three): (1) it follows a reasonable temporal sequence from administration of the study treatment. (2) It could not readily have been produced by subject's clinical state, environmental or toxic factors, or other therapies administered to the subject. (3) Disappears or is decreased upon discontinuation of the study treatment. (4) It follows a known response pattern to treatment with the study treatment.
- Possibly related:** This category applies to those AEs which, after careful medical consideration at the time they are evaluated, are judged unlikely but cannot be ruled out

with certainty to the study treatment. An AE may be considered possible if or when (must have two): (1) it follows a reasonable temporal sequence from administration of the study treatment. (2) It could not readily have been produced by subject's clinical state, environmental or toxic factors, or other therapies administered to the subject. (3) Disappears or is decreased upon discontinuation of the study treatment. (4) It follows a known response pattern to treatment with the study treatment.

4. **Unlikely related:** In general, this category can be considered applicable to those AEs which, after careful medical consideration at the time they are evaluated, are judged likely to be unrelated to the study treatment. An AE may be considered unlikely if or when (must have two): (1) it does not follow a reasonable temporal sequence from administration of the study treatment. (2) It could not readily have been produced by subject's clinical state, environmental or toxic factors, or other therapies administered to the subject. (3) Disappears or is decreased upon discontinuation of the study treatment. (4) It does not follow a known response pattern to treatment with the study treatment.
5. **Unrelated:** This category applies to those AEs which, after careful consideration at the time they are evaluated, are clearly and incontrovertibly due to extraneous causes (disease, environment, etc.) and determined with certainty to have no relationship to the study treatment.

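### Two of the four Unlikely related criteria in Protocol 8.3.3.2 are left un-negated, so evidence that favours causality can satisfy the Unlikely checklist

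*Protocol*

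**What the plan says.** Protocol 8.3.3.2 defines five causality categories. Three of them use the same four attributes: timing, absence of another ready cause, improvement on stopping the drug (dechallenge), and a known response pattern.

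- **Probably related.** The lead-in covers events that "are felt with a high degree of certainty to be related to the study treatment". The rule is "An AE may be considered probable if or when (must have three") of the four attributes, all worded in favour of causality.
- **Possibly related.** The lead-in covers events that "are judged unlikely but cannot be ruled out" with certainty. The rule is "An AE may be considered possible if or when (must have two") of the same four attributes in the same direction.
- **Unlikely related.** The lead-in covers events that "are judged likely to be unrelated to the study treatment". The rule is "An AE may be considered unlikely if or when (must have two") of four items. Items (1) and (4) are negated. Item (2) repeats the Probably/Possibly wording, and so does item (3), as the text shows: "3) Disappears or is decreased upon discontinuation of the study treatment. (4) It does not follow a known response pattern".

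Definitely related requires timing, no other reasonable explanation and a known pattern together. Unrelated has no checklist. The section also says "The Investigator will be responsible for determining the relationship between an AE and the study treatment".

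SAP 10.1 counts Possibly, Probably and Definitely as drug-related, and Unlikely and Unrelated as not related. Protocol section 3 and SAP 3.3 name relationship to study therapy as part of the primary endpoint.

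**The concern.** Absence of another cause and a positive dechallenge are evidence for causality. In the Unlikely list they count towards a category whose lead-in says the opposite. An event with exactly these two findings meets two of four for Possibly and also two of four for Unlikely.

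That boundary is where the SAP divides drug-related from not drug-related events. Two investigators, or one investigator on two days, could follow the text and place the same event on different sides. The same boundary is used in Protocol 4.3 (study stopping) and 6.1.4 (treatment discontinuation), both of which refer to possibly or probably related laboratory events.

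**Working it through.** The plan states no figure on this point, so the check is a full enumeration of the checklists.

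**Inputs (Protocol 8.3.3.2).** Score each attribute 1 (yes) or 0 (no): T = reasonable timing, N = not readily produced by another cause, D = disappears or decreases on discontinuation, K = known response pattern. This gives 2^4 = 16 patterns.

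**Rules, reading each threshold as a minimum.**
- R = T + N + D + K. Possibly: R ≥ 2. Probably: R ≥ 3. Definitely: T = N = K = 1.
- Unlikely as written: U = (1−T) + N + D + (1−K) ≥ 2.
- Unlikely with (2) and (3) negated: U′ = (1−T) + (1−N) + (1−D) + (1−K) = 4 − R ≥ 2.

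| Patterns (TNDK) | R | U as written | U′ |
|---|---|---|---|
| 1111 | 4 | 2 | 0 |
| 1110, 0111 | 3 | 3 | 1 |
| 1101, 1011 | 3 | 1 | 1 |
| 1100, 1010, 0101, 0011 | 2 | 2 | 2 |
| 0110 | 2 | 4 | 2 |
| 1001 | 2 | 0 | 2 |
| 0100, 0010 | 1 | 3 | 3 |
| 1000, 0001 | 1 | 1 | 3 |
| 0000 | 0 | 2 | 4 |

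**As written.**
- Both a related category and Unlikely (R ≥ 2 and U ≥ 2): 1 + 2 + 4 + 1 = 8 patterns.
- Of these 8, three meet Probably (1111, 1110, 0111). One of the three, 1111, has every pro-causal feature and also meets Definitely. The other five meet Possibly only.
- No list met (R < 2 and U < 2): 2 patterns, 1000 and 0001.
- Pattern 0110, whose only positive findings are the two un-negated items, scores the maximum of 4 on the Unlikely list.

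**If the thresholds meant exactly two or exactly three.** The Probably/Unlikely overlap disappears. Five patterns still cross the SAP line (1111 through Definitely; 1100, 1010, 0101 and 0011 through Possibly), and 4 meet no list. The defect does not depend on the reading.

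**With (2) and (3) negated, thresholds as minimums.**
- Probably and Unlikely: 3 falls to 0. Definitely and Unlikely: 1 falls to 0. No list met: 2 falls to 0.
- Possibly and Unlikely: all 6 patterns with R = 2 now tie, because U′ = 4 − 2 = 2. Five of these overlap today; the sixth, 1001, becomes a tie through the negation.
- If the thresholds are instead read as exact, 6 ties and 5 unclassified patterns result. The meaning of the threshold therefore has to be stated as well.

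**When dechallenge cannot be assessed.** This can happen, because dosing ends on Day 5 while events are collected to the Day 14 visit. If D is left out on both sides, 8 patterns remain. As written, 2 of them still meet both Possibly and Unlikely (TNK = 110 and 011), and 2 meet no list (100 and 001).

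**The case against.** The strongest reply is that the checklists do not decide anything. The investigator assigns causality, the lists say only that an event may be considered to fall in a category, and each category opens with a judgement. An investigator who follows the lead-ins would not code an event with all four pro-causal features as Unlikely. This stands, and it largely protects the Probably and Definitely boundaries. It protects Possibly against Unlikely less well, because the Possibly lead-in itself uses the word unlikely.

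The reach is also limited. The study is open-label and descriptive, with 30 subjects and no planned inference. Relationship is tabulated by category (SAP Table 14.3.1.5), treatment-emergent events are tabulated regardless of relationship, and each event is listed individually. The independent DMC receives both the by-relationship table and the individual listing. SAE reporting does not depend on causality. All of this stands, but these outputs display the assigned category and do not correct the rule behind it.

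A reader might infer that the error lowers the count of drug-related events, or that about half of the events will be misclassified. The documents support neither. The enumeration weights 16 patterns equally and says nothing about how often each occurs, and no direction or size of effect on the counts can be derived.

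A reader might also infer that the Unlikely threshold should be raised, or that an unassessable dechallenge should be scored as absent. Those are choices of scale design. Raising the threshold would send every tie to Possibly and so change what Protocol 4.3 and 6.1.4 capture. Scoring missing dechallenge as absent would count missing evidence towards not related. Neither choice follows from the wording error.

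**Conclusion.** The point holds as a wording error in a classification rule. Items (2) and (3) of Unlikely related point the opposite way from their own lead-in. On the checklists alone, 8 of 16 patterns qualify for both a related category and Unlikely, and 2 qualify for none. Negating the two items removes the clear contradictions but leaves 6 Possibly/Unlikely ties, which come from using two of four on both lists.

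The counts assume that each criterion is scored yes or no, that the thresholds are minimums, and that the no-other-explanation criterion in Definitely is the same attribute as in the other lists. They leave out the lead-ins. Overlap among Definitely, Probably and Possibly is nested and is not at issue here, since all three fall on the same side of the SAP split.

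The SAP introduction also cites protocol clarification letter #01, which was not available for this review; whether it touches 8.3.3.2 is unknown. The severity is minor to moderate: the boundary affected carries part of the primary endpoint, but nothing in the text forces an event to be miscoded.

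**What to change.** In one amendment to Protocol 8.3.3.2:

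- Reword Unlikely item (2) to say that the event could readily have been produced by the listed other causes.
- Reword Unlikely item (3) to say that the event does not disappear or decrease when study treatment is stopped.
- State that each threshold is a minimum.
- State how an event with two points for and two against is classified. The sponsor should choose the rule, and should also say how an unassessable dechallenge is handled. Neither rule is prescribed here.

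Two separate inconsistencies should be settled at the same time. Protocol 9.7.4.2 lists a category called remotely, which the scale does not contain. Protocol 4.3 and 6.1.4 name only possibly and probably related events although the scale also has Definitely. Both sections must be reconciled with the corrected scale, including any effect of the tie rule; no stopping or discontinuation rule is proposed.

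The cost is a wording amendment with IRB approval. Protocol 12.2 and 13.1 exempt changes that do not involve subject participation, but this exemption may not apply because causality feeds 6.1.4. Events already coded need a re-check. In an open-label study this carries some risk of hindsight bias, so both the existing and the revised code should stay on record. No extra subjects or procedures are needed.

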8.3.3.3. Expectedness

The Medical Monitor will be responsible for determining whether an AE is expected or unexpected. An AE will be considered unexpected if the nature, severity, or frequency of the event is not consistent with the information described in the Investigator's Brochure.

Refer to the Investigator's Brochure for the expected/anticipated events.

8.3.4. Reporting of AEs

Report initiation for all AEs and SAEs will begin at the time of the first treatment visit and continue until the end of final study visit. All events will be followed to resolution or until the subject completes the study. A final assessment of outcome will be made at that time.

All AEs must be recorded in the subject's study records. AEs will be reported using customary medical terminology along with the following information: the onset and end dates, whether the event is considered to be a SAE (see Section 8.3.2), the impact the event had on study treatment (see Section 8.3.4.1), the Common Terminology Criteria for Adverse Events (CTCAE) grade (intensity) of the event (see Section 8.3.3.1), the causality of the event (see Section 8.3.3.2, whether treatment was given as a result of the event (see Section 8.3.4.2), and the outcome of the event. (see Section 8.3.4.3).

8.3.4.1. Impact on Study Treatment

The impact the event had on the study treatment will be assessed as either: dose increased, dose not changed, dose rate reduced, dose reduced, drug interrupted, drug withdrawn, not applicable, or unknown. The “not applicable” assessment will be used only when the subject is no longer in the Treatment Phase of the protocol.

8.3.4.2. Treatment Given as a Result of the Event

The event impact in terms of treatment provided will be as either: none, medication administered, non-drug therapy administered, surgery performed, hospitalization, or other (with a specification).

8.3.4.3. Outcome Assessment

The outcome of the event will be assessed as either: fatal, not recovered/not resolved, recovered/resolved, recovered/resolved with sequelae, recovering/resolving, or unknown. Only one AE per subject is allowed to have an outcome assessment as “death.” If there are multiple causes of death for a given subject, only the primary cause of death will have an outcome of death.

8.3.5. Reporting of SAEs

The Investigator is required to report all SAEs that occur during the time period specified in Section 8.3.4. Once the Investigator becomes aware of an SAE, he/she must report the SAE to Sponsor’s Contract Research Organization (CRO) Safety Department within 24 hours.

Safety Department	

The designee in Safety Department may request additional supporting documentation as it becomes available, such as lab reports, electrocardiogram [ECG] reports, discharge summary, hospital notes, etc., if applicable. Additional follow-up information as it becomes available must be reported to the designee in Safety Department.

The Investigator is also responsible for reporting all SAEs to the appropriate Institutional Review Board (IRB) in accordance with local laws and regulations. The Investigator is responsible for maintaining documentation in the study file that indicates the IRB has been properly notified.

